5.0 SUBJECT REGISTRATION

All patients who are consented will be entered into the UCSF Cancer Center OnCore® database. The OnCore® database is password protected and meets HIPAA guidelines.

To register patients on-study, study personnel will complete an eligibility form. Study ID numbers for each patient will be assigned serially. Pertinent information will be entered from the patient medical record.

6.0 TREATMENT PLAN

Segmental hepatic artery catheterization will be performed via femoral artery approach using a combination of 3-French, 4-French, and 5-French angiographic catheters. Segmental DEB-TACE will be performed using two 2ml vials of LC beads (Biocompatibles, Inc.) impregnated per standard manufacturer-supplied protocol with a total of 100 mg of doxorubicin (25 mg per milliliter of beads). Microspheres in the size range of 100-300 μ m will be used. Procedure will be stopped when arterial flow approaches stasis and/or when the entire DEB dose has been administered.

Patients with multiple liver lesions, lesions >3 cm, or lesions with more than 1 feeding branch hepatic artery may receive additional DEB-TACE at approximately 1 month intervals. Cross-sectional imaging (contrast-enhanced CT or MRI) will be performed approximately 1 month after targeting of all hepatic lesions in the course of 1-4 DEB-TACE procedures. Patients with residual or recurrent disease may receive up to 4 total DEB-TACE procedures.

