Imaging Studies												
Contrast-Enhanced CT or MRI of the abdomen	X											
CT chest with and/or without contrast	X											
Cardiac Function Assessment												
Echocardiogram	X ^{&}					X ^{&}			X ^{&}			X ^{&}
DEB-TACE Procedure												
DEB-TACE**			X			X**			X**			X**
Pharmacokinetics Evaluation												
Pharmacokinetics data acquisition***			X	X	X							

Abbreviation: d = days

* See Table 2 for post-treatment evaluation after DEB-TACE 4. DEB-TACE 3 and 4 are optional for patients with disease extent limited to two liver segments. Patients may proceed to evaluation of response and long-term follow-up after fewer than 4 DEB-TACE treatments at the investigator's discretion.

& Cardiac function will be assessed via echocardiogram at baseline and one month following last planned DEB-TACE.

** Up to 4 DEB-TACE procedures may be performed at approximately 1 month intervals depending upon initial size, number, vascular supply of lesion(s) and interval treatment response on imaging.

*** See plan for pharmacokinetic data acquisition in Sections 8.1 and 8.4

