12.0 STATISTICAL CONSIDERATIONS

12.1 Basis for Sample Size

This is an open label single arm phase II study. The primary objective is to assess the safety and to estimate the objective response rate using mRECIST in treated lesions to the DEB-TACE treatment. The response rate is assumed to be >40% in treated lesions using mRECIST on imaging approximately 1 month after last planned DEB-TACE treatment; the response rate of <20% would be unacceptable for the study treatment. If the response rate is less than a pre-specified minimum goal (i.e. 20%) then the study will be terminated due to inefficacy. Under binomial approximation with 5% type I error and 85% power, a total of 51 patients is required for the study; 17 patients will be accrued in the first stage and 34 patients will be accrued in the second stage.

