12.3 Analysis Plan

Demographics and Baseline Characteristics

Demographic and baseline laboratory results will be summarized using descriptive statistics.

Safety Analysis

Patients will be monitored for development of recognized complications of DEB-TACE including liver dysfunction, renal dysfunction, ascites, hepatic encephalopathy, hepatorenal syndrome, biliary injury (stricture or leak), cholangitis, cholecystitis, hepatic abscess, abdominal pain, nausea, vomiting, fatigue, and fever. Adverse events will be graded according to NCI CTCAE version 4.03. Prevalence of adverse events will be summarized using descriptive statistics.

Efficacy Analyses

Analyses will be performed using the intent to treat population with exceptions as defined below, which require patient replacement.

Primary efficacy analysis

Primary efficacy will be evaluated as 1-month radiographic response after last DEB-TACE procedure in treated HCC lesions according to 1) RECIST version 1.1 and 2) mRECIST. Patients who do not have any post-baseline tumor assessments will be counted as non-responders. Point estimates of response rate and confidence intervals will be provided.

Secondary efficacy analyses

1. Overall radiographic response by 1) RECIST 1.1 and 2) mRECIST 6 months after the date of the first planned DEB-TACE procedure. This analysis will take into account all measurable hepatic HCC lesions present on cross-sectional imaging 6 months after the date of the first planned DEB-TACE procedure.
2. Time to untreatable progression (TTUP). TTUP is defined as time to disease progression untreatable by liver-directed percutaneous or surgical methods as assessed by treating investigator(s). Patient follow-up up to 1 year after last DEB-TACE will be allowed for this outcome variable.
3. Time to progression (TTP). TTP is defined as the time interval between date of first DEB-TACE procedure and date of imaging documenting development of intra- or extrahepatic disease progression by 1) RECIST 1.1 and 2) mRECIST. Patient follow-up up to 1 year after last DEB-TACE will be allowed for this outcome variable.

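### Section 12.3 reads the primary response after the last procedure, not the last planned one, so retreatment for residual disease can move the read

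*Combined protocol and SAP*

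**What the plan says.** Section 12.3 (Analysis Plan, primary efficacy analysis) states: "Primary efficacy will be evaluated as 1-month radiographic response after last DEB-TACE procedure in treated HCC lesions". The word *planned* is absent.

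The other sections that define or use this endpoint include it. Section 12.1 sets the target as "The response rate is assumed to be >40% in treated lesions using mRECIST" and ties it to assessment "on imaging approximately 1 month after last planned DEB-TACE treatment". The interim and final rules in 10.2 and 12.2, and the efficacy section 9.2, also refer to the last planned procedure. Section 9.2 adds that the scan falls within six months of the first procedure.

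Two passages let treatment continue in the light of response:

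- Section 6.0 places imaging about a month after all lesions have been targeted, then says: "Patients with residual or recurrent disease may receive up to 4 total DEB-TACE procedures".
- A Table 3 footnote (Section 8.0) allows up to four procedures, "depending upon initial size, number, vascular supply of lesion(s) and interval treatment response on imaging". Another footnote lets patients move to response evaluation after fewer than four sessions, at the investigator's discretion.

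Sections 8.4.1, 8.4.2 and 10.3 remove a patient for retreatment with DEB-TACE only when more than four procedures are needed. No section says when the plan is fixed, or whether a session given after the response scan resets the primary read.

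**The concern.** Under the wording of 12.3, the primary read follows whichever session turns out to be last. A patient whose first response scan shows failure can have another session, stay on study and be read again. Under the planned wording in 10.2 and 12.2, the same patient would arguably be counted on the first scan. One patient could therefore be a non-responder for the decision rule and a responder in the primary analysis.

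The planned wording alone does not settle this, because no section requires the plan to be recorded before its outcome is known. The study is open-label, and Section 8.4.2 leaves delay or cancellation of planned sessions to the treating physicians.

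At stake is the go/no-go decision. The cut-offs are calibrated to a fixed probability of response per patient. If that probability includes second chances that the null rate did not, the stated type I error no longer describes the trial.

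**Working it through.** **Inputs from the plan.** Section 12.1: "Under binomial approximation with 5% type I error and 85% power, a total of 51 patients is required for the study"; "the response rate of <20% would be unacceptable for the study treatment", so p0 = 0.20; target p1 = 0.40; "17 patients will be accrued in the first stage and 34 patients will be accrued in the second stage". Sections 10.2 and 12.2: stop at 4 or fewer responses in 17; no further investigation at 14 or fewer in 51. Success therefore needs at least 5 of 17 and at least 15 of 51.

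**Step 1: reproduce the design (exact binomial).**

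P(stop at stage 1 | p) = P(Bin(17, p) ≤ 4)

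P(success | p) = Σ over x = 5 to 17 of P(Bin(17, p) = x) × P(Bin(34, p) ≥ 15 − x)

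| Quantity | Computed | Stated |
|---|---|---|
| Stage 1 stop at p = 0.20 | 0.758 | 76% |
| Stage 1 stop at p = 0.40 | 0.126 | 13% |
| Success at p = 0.20 (type I error) | 0.0487 | 5% |
| Success at p = 0.40 (power) | 0.854 | 85% |

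The plan's figures are correct for one response probability per patient.

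**Step 2: let retreatment precede the read.** Suppose 20% is the response rate before retreatment. Let f be the share of non-responders retreated once and c the chance that a retreated non-responder becomes a responder. The documents give neither value; both are assumptions. The effective rate is

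p_e = 0.20 + 0.80 × f × c

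and the false-positive rate is P(success | p_e).

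| f | c | p_e | P(success) |
|---|---|---|---|
| 0.25 | 0.10 | 0.20 + 0.80 × 0.025 = 0.22 | 0.095 |
| 0.50 | 0.10 | 0.20 + 0.80 × 0.05 = 0.24 | 0.161 |
| 0.25 | 0.20 | 0.20 + 0.80 × 0.05 = 0.24 | 0.161 |
| 0.50 | 0.20 | 0.20 + 0.80 × 0.10 = 0.28 | 0.348 |
| 1.00 | 0.20 | 0.20 + 0.80 × 0.20 = 0.36 | 0.734 |

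The last row is an extreme: every non-responder is retreated, and each has the same chance as the first time.

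**Step 3: the other reading of 20%.** If 20% is the unacceptable rate for the whole course of up to four sessions, retreatment included, then p_e = 0.20 by definition and the false-positive rate stays at 0.0487.

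**Step 4: with the read fixed at the first scan after the planned course.** Later sessions cannot alter the result. With 20% and 40% defined at that read, Step 1 applies: type I error 0.0487, power 0.854, N = 51.

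**The case against.** The best defence is that 12.3 is the outlier. The sample size basis, both decision rules and the efficacy section all refer to the planned procedure. Sections 3.2 and 8.3 describe the sessions as a stepwise course, set by lesion number, location and size and by arterial supply, and completed before response is assessed. Table 3 schedules no abdominal scan between sessions, and its footnote lists anatomical factors before interval response. This stands: response-driven retreatment is a route left open, not the main design.

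A reader might infer that the 5% type I error is broken. The documents do not support that. Section 12.1 ties its target to the scan after the last planned treatment, and the source of the 20% is not given. If the 20% describes the same whole course, nothing is inflated.

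A reader might also infer that only failures are retreated while responders are read once. That goes too far. A partial responder also has residual disease and qualifies under Section 6.0. Section 10.2 counts stable disease as a response, so on that definition only patients with progression or without an assessment could be converted. Section 12.1 speaks of objective response, which would leave stable patients convertible too.

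Re-eligibility before each session (3.2, 4.2), the four-session cap, removal for untreatable progression, other therapy or transplant (10.3) and the six-month limit (9.2) all restrict retreatment, so the 73% case is not a realistic expectation.

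None of this removes the conflict between 12.3 and the other sections, or supplies a rule for a patient retreated after the response scan.

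**Conclusion.** The inconsistency is real and affects the primary endpoint. Section 12.3 and Sections 9.2, 10.2, 12.1 and 12.2 can classify the same retreated patient differently, and Section 6.0 with the Table 3 footnote makes such patients possible.

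The statistical consequence is conditional. If the 20% null is a rate before retreatment, the false-positive rate exceeds the design's 4.9%: 9.5% at an effective rate of 22%, 16% at 24% and 35% at 28%. If the 20% covers the whole course including retreatment, it stays at 4.9%. The documents do not say which applies. The retreated share and the conversion chance behind these effective rates are assumptions, so the figures show sensitivity and are not estimates. A flat statement that the type I error is inflated is not supported.

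**What to change.** 1. In 12.3, refer to the last planned procedure, to match 9.2, 10.2, 12.1 and 12.2.
2. Record the planned number of sessions no later than the end of the first procedure. An earlier deadline would not work, because Section 3.2 uses hepatic angiography to set the number and Section 3.1 performs the angiogram as part of the procedure.
3. Define the primary response as the first scan about one month after the last session of that course actually given, within six months of the first procedure. If planned sessions are cancelled, as 8.4.2 allows, count from the last one delivered.
4. State that DEB-TACE given for residual or recurrent disease seen on that scan does not change the primary result. Report response after such retreatment as secondary.
5. State in 12.1 that the 20% and 40% rates refer to this read.

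One related conflict bears on item 3. Section 8.3 allows gaps of up to 90 days, so four sessions can span 3 × 90 = 270 days, beyond the six-month limit in 8.4.2 and 9.2. These passages must be reconciled.

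The cost is protocol and SAP wording and one form field. Treatment and N = 51 do not change. The reported response rate may be slightly less favourable.

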7.0 TOXICITY MANAGEMENT

Once they are enrolled in the study, patients will be discussed at the gastrointestinal oncology site committee meeting at bi-weekly intervals for the first month following each DEB-TACE treatment. Any adverse events grade ≥ 4 will be discussed by the interventional radiologist and medical oncologist or hepatologist within 24 hours of being informed of the event.

7.1 Liver toxicity

Up to one half of the patients are expected to experience at least one liver-related side effect following DEB-TACE. Liver-related toxicities, for which all patients will be monitored include elevation the serum bilirubin level, increase in aspartate or alanine aminotransferase, development of ascites, hepatic encephalopathy, hepatorenal syndrome, liver failure, hemobilia, gastrointestinal hemorrhage, cholangitis, liver abscess, and bile duct stricture. Most of these toxicities (80%) are expected return to pre-treatment levels. However, some may persist and may be exacerbated by tumor progression and/or advancing cirrhosis. Risk of liver toxicity will be minimized by performing segmental or subsegmental DEB-TACE whenever possible.

Patients will be screened for presence of laboratory liver function test abnormalities at 10-day intervals for the first month following each DEB-TACE treatment. Any abnormal lab values will be followed as clinically indicated. Patients with ascites will be followed clinically and will be treated if symptoms referable to ascites develop. Patients with hepatic encephalopathy,

hepatorenal syndrome, liver failure, hemobilia, gastrointestinal hemorrhage, cholangitis, liver abscess, and bile duct stricture will be treated according to the current standard of care.

7.2 Renal toxicity

Renal toxicity may be related to administration of iodinated contrast at the time of DEB-TACE or to development or exacerbation of the hepatorenal syndrome. Renal toxicity is expected to occur in fewer than 10% of patients. If renal impairment occurs, patients will be treated medically. Renal replacement therapy will be initiated if clinically indicated.

7.3 Postembolization syndrome

A combination of abdominal pain, nausea/vomiting, fever, fatigue, and anorexia constitutes the post-embolization syndrome. The risk of postembolization syndrome related to DEB-TACE is estimated at 50-70%. While the risk of post-embolization syndrome is high, the symptoms are usually self-limited after a period of 10-14 days. Symptoms are expected to be most severe within the first 24 hours of DEB-TACE. Therefore, all patients will be admitted for 23-hour inpatient observation as per standard of care at UCSF for intravenous fluids, analgesic, and antiemetic therapy. Upon discharge, patients will be given a prescription for oral opiate analgesic and antiemetic agents.

7.4 Side effects of angiography and embolization

Side effects of angiography may include access site hematoma, arterial injury (dissection, thrombosis) related to catheter or wire manipulation, allergic reactions to iodinated contrast (rash, dyspnea, hypotension, cardiopulmonary arrest), and contrast-induced nephropathy. The risks of angiography are small, with access site hematoma being the most common side effect occurring in < 5% of patients.

7.5 Drug-drug interactions

Patients who are receiving P-glycoprotein inhibitors and CYP2D6 substrates that have a narrow therapeutic index for the potential risk of increased adverse events. However this risk of a drug interaction with systemically administered drugs might be low following intra-arterial bead-bound doxorubicin as compared to intravenous administration of doxorubicin.

Because of possible hepatotoxic and nephrotoxic effect of TACE, concurrent use of hepatotoxic and nephrotoxic drugs will be avoided.

8.0 EVALUATIONS AND PROCEDURES

Table 2 Schedule of Events: Single Deb-TACE

	Pre-treatment		DEB-TACE	Post Treatment Evaluation							
	Screening Evaluation	-60 to 0 days		-6 ± 6d	Day 0	1 ± 0d	7 ± 4d	30 ± 7d	90 ± 14d	180 ± 14d	270 ± 14d
Clinical/Administrative Activities											
Informed Consent	X										
Demographics	X										
Medical History	X										
Physical Examination	X	X									
ECOG Performance Status (See Appendix 1)	X	X				X	X	X	X	X	
Child Pugh Turcotte Score (See Appendix 2)	X					X	X	X	X	X	
MELD Score (See Appendix 3)	X					X	X	X	X	X	
Interim History + Physical Exam					X*	X	X	X	X	X	
Evaluation of Response						X	X	X	X	X	
Laboratory Tests											
CBC, Coagulation Panel, BUN, Creatinine, Liver Function Tests	X	X			X	X	X	X	X	X	
Alpha-fetoprotein		X				X	X	X	X	X	
Imaging Studies											
Contrast-Enhanced CT or MRI of the abdomen	X					X	X	X	X	X	
CT chest with and/or without contrast	X						X	X	X	X	
Cardiac Function Assessment											
Echocardiogram	X&						X&				
DEB-TACE Procedure											
DEB-TACE			X								
Pharmacokinetics Evaluation											
Pharmacokinetics sample acquisition**			X	X	X						

Abbreviation: d = days

* May be substituted by telephone follow-up by interventional radiology nurse practitioner for patients who are non-local study participants.

& Cardiac function will be assessed via echocardiogram at baseline and one month following last planned DEB-TACE.

** See plan for pharmacokinetic data acquisition in Sections 8.1 and 8.4

Table 3 Schedule of Events: Multiple DEB-TACE procedures*

	Pre-treatment Evaluation	DEB-TACE 1	Evaluation TACE 1	DEB-TACE 2	Evaluation TACE 2	DEB-TACE 3	Post Treatment Evaluation TACE 3	DEB-TACE 4**				
	-60 to 0 days	-6 ± 6d	Day 0	1d	7 ± 4d	30 +30d (Reset to d0)	1d	7 ± 4d	30 +30d (Reset to d0)	1	7 ± 4d	30 +30d (Reset to d0)
Clinical / Administrative Activities												
Informed Consent	X											
Demographics	X											
Medical History	X					X			X			X
Physical Examination	X	X										
ECOG Performance Status	X	X				X			X			X
Child Pugh Turcotte Score (See Appendix 2)	X											
MELD Score (See Appendix 3)	X					X			X			X
Interim History + Physical Exam					X	X		X	X		X	X
Laboratory Tests												
CBC, Coagulation Panel, BUN, Creatinine, Liver Function Tests	X	X		X	X	X	X	X	X	X	X	X
Alpha-fetoprotein		X										
Imaging Studies												
Contrast-Enhanced CT or MRI of the abdomen	X											
CT chest with and/or without contrast	X											
Cardiac Function Assessment												
Echocardiogram	X ^{&}					X ^{&}			X ^{&}			X ^{&}
DEB-TACE Procedure												
DEB-TACE**			X			X**			X**			X**
Pharmacokinetics Evaluation												
Pharmacokinetics data acquisition***			X	X	X							

Abbreviation: d = days

* See Table 2 for post-treatment evaluation after DEB-TACE 4. DEB-TACE 3 and 4 are optional for patients with disease extent limited to two liver segments. Patients may proceed to evaluation of response and long-term follow-up after fewer than 4 DEB-TACE treatments at the investigator's discretion.

& Cardiac function will be assessed via echocardiogram at baseline and one month following last planned DEB-TACE.

** Up to 4 DEB-TACE procedures may be performed at approximately 1 month intervals depending upon initial size, number, vascular supply of lesion(s) and interval treatment response on imaging.

*** See plan for pharmacokinetic data acquisition in Sections 8.1 and 8.4

8.1 Screening/Baseline

Prior to enrollment, patients will be seen by a hepatologist and/or a medical oncologist at UCSF and evaluated for all possible treatment options, one of which will include DEB-TACE. Prior to enrollment, all patients will be discussed in the multidisciplinary liver tumor board, which

includes hepatologists, medical and surgical oncologists, and interventional radiologists. If the patient is deemed a good candidate for the procedure, the patient will then be referred to the interventional radiologist for DEB-TACE. Patients will be offered the opportunity to be screened for study participation. After informed consent is obtained, pre-procedure assessment is summarized in Table 1.

Approximately zero to sixty days prior to DEB-TACE, the following will be performed to determine eligibility:

- cross sectional imaging of the abdomen using multi-phase CT or MRI with IV contrast
- CT scan of chest (with and/or without contrast)
- baseline laboratory tests
- clinical history and physical examination

Approximately zero to twelve days prior to DEB-TACE, the following additional procedures will be performed (if the initial screening is performed outside 12-day window):

- Laboratory testing including liver function tests, CBC, BUN, creatinine, coagulation profile, and serum alpha-fetoprotein level
- Medical history and physical examination
- ECOG performance status

Baseline cardiac function monitoring using echocardiogram will be performed approximately zero to 720 days prior to first planned DEB-TACE

One day prior to DEB-TACE, the UCSF Inpatient Pharmacy will be instructed by the interventional radiologist to start incubation of two 2ml vials of 100-300 μ LC Beads[®] with 100mg doxorubicin (25mg/ml of beads) per manufacturer-supplied instructions for use (currently not cleared by the FDA for use).

8.2 Treatment

The patient will come directly to the Interventional Radiology on the day of the procedure after an overnight fast. Moderate sedation will be supervised by the interventional radiologist performing the procedure. The patients will be continuously monitored during the procedure by an IR nurse. Access to the hepatic artery will be achieved using an angiographic catheter placed in the femoral artery. An angiographic catheter will be directed under fluoroscopic guidance to the appropriate location in the hepatic artery. Doxorubicin-loaded LC beadTM will be mixed with non-ionic iodinated contrast (per manufacturer-supplied instructions for use) and administered into the target hepatic artery branch under continuous fluoroscopic guidance by the interventional radiologist until flow approaches stasis or until the entire DEB dose is administered.

The investigators will estimate the total amount of doxorubicin administered for each DEB-TACE procedure using the following formula:

$$\text{Doxorubicin dose} = 0.98 * 50\text{mg} * [\% \text{ of vial 1 delivered} + \% \text{ of vial 2 delivered}] / 100$$

In the formula, correction factor 0.98 accounts for incomplete absorption of doxorubicin to LC Bead™, while 50 mg is the doxorubicin dose to be mixed with each 2 ml vial of beads.

Estimated doxorubicin dose will be recorded in patients' study charts and will be recorded in the medical record.

Pharmacokinetics data for doxorubicin will be collected by obtaining peripheral venous blood samples from the first 17 patients at the time of completion of the first planned DEB-TACE, and subsequently 5±1 min, 30±5 min, 60±5 min, 120±10 min, 6±0.5 hours, 20±2 hours, and 8±2 days following administration of 100-300 mm doxorubicin-impregnated LC bead™.

All patients will be admitted to the hospital for planned 23-hour observation upon completion of the procedure and will then be discharged home once determined to be in stable condition. Management after each DEB-TACE procedure will be according to institutional standard of care.

